#### 8.4.2 Analysis of the Primary Efficacy Endpoints

The average of the AUC values at the 4 determinations associated with each of the two drug administrations will be determined and the difference assessed for statistical significance at the 0.05 level using the non-parametric procedures identified in the Koch 1972 paper.

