## 3 STUDY IMPLEMENTATION

### 3.1 STUDY DESIGN

This is a randomized, open-label, single-dose, 2-way crossover, pilot bioavailability trial evaluating two oral formulations of enzalutamide. All men (n=12-14) enrolled in the trial will receive oral enzalutamide in two formulations: Treatment A will be the standard liquid-filled, soft gelatin capsule (reference) formulation; Treatment B will be the liquid formulation (test product). Subjects will be randomized in Period 1 to one of two sequences: AB or BA. Following a minimum 42-day washout period, subjects will be crossed over in Period 2 to receive the treatment that they did not receive in Period 1. Blood samples will be collected for pharmacokinetic analysis.

Subjects are admitted to the Clinical Center on Day 1 (for the first 24-hours of PK sampling) and will take a single 160mg dose of enzalutamide. They are to return to the Clinical Center on Day 3 for the 48h, on Day 8 for the 168h, and Day 42 for the post-dose blood draws. After an appropriate washout period (at least 42 days), subjects will be crossed over in Period 2 to receive the treatment that they did not receive in Period 1. Subjects will be re-admitted to the Clinical Center to receive the study drug and blood samples will be drawn as described above on Days 1, 3, 8, and 42. Drug Administration

*Abbreviated Title: Enzalutamide Formulation PK*  
*Version Date: 03.11.2020*

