## 5 BIOSPECIMEN COLLECTION

### 5.1 CORRELATIVE STUDIES FOR RESEARCH/PHARMACOKINETIC STUDIES

The time of enzalutamide dose administration is  $t = 0$  for purposes of pharmacokinetic sample collection times. Due to the long  $t_{1/2}$  of enzalutamide, *N*-desmethyl enzalutamide, and the carboxylic acid metabolite in healthy subjects (approximately 6, 8, and 10 days, respectively [7]), pharmacokinetic samples will be collected over 42 days.

With each 160 mg dose of enzalutamide, pharmacokinetic blood samples will be collected in 6-mL tubes with dipotassium ethylenediaminetetraacetic acid (K2 EDTA) as the anticoagulant. Venous blood samples for plasma will be collected at the following times: pre-dose (0 hr) and post-dose at 30 minutes; and at 1, 2, 4, and 8 hours (Day 1), 24h (Day 2), 48h (Day 3), 168h (Day 8), and Day 42 post-dose.

Validated bioanalytical methods based on ultra high-performance liquid chromatography with tandem mass spectrometry (uHPLC-MS/MS) [10] will be developed by the Clinical Pharmacology Program and used to analyze plasma samples for concentrations of enzalutamide and the two major human metabolites (e.g. *N*-desmethyl enzalutamide and carboxylic acid enzalutamide).

Non-compartmental PK analysis of enzalutamide in plasma will be performed using WinNonlin 5.0 (Pharsight, Inc., Mountain View, CA). PK parameters derived from plasma concentration-time data may include  $C_{max}$ ,  $T_{max}$ , AUC, Cl, Cl/F, Vd, and  $t_{1/2}$ .

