## **8 STATISTICAL CONSIDERATIONS**

### **8.1 STATISTICAL HYPOTHESES**

#### **Primary efficacy endpoints:**

To evaluate the bioequivalence of two oral formulations of enzalutamide following a single 160 mg dose in male subjects with prostate cancer.

The primary measure of efficacy will be AUC for the first period of administration obtained during blood draws during visits on day 1, 3, 8, and 42 evaluations, and then AUC at a second set of visits at least 42 days after the first administration, for evaluations on days 1, 3, 8 and 42 relative to the second administration, for the second period evaluations.

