### **8.2 SAMPLE SIZE DETERMINATION**

This study will be conducted as a two-period randomized crossover trial design. Patients will be randomized to initially receive the standard liquid filled soft gelatin formulation (Arm A) followed later by the liquid formulation, or the liquid formulation as the test product (Arm B)

Abbreviated Title: Enzalutamide Formulation PK  
Version Date: 03.11.2020

followed by the liquid filled soft gelatin formulation. A total of 12 evaluable patients will be randomized into the two arms. It has been identified that a decrease of approximately 30-40 ug\*h/mL in the AUC (less than a 20% decrease in the AUC for the test version vs. the standard formulation) would permit the two formulations to be considered bioequivalent, and it may be expected that the actual difference between the formulations may be a decline of approximately 10% (approximately 20 ug\*h/mL). When the sample size in each sequence arm is 6, (a total sample size of 12) a crossover design will have 80% power to reject the null hypothesis that the Arm B mean minus the Arm A mean is below -40 ug\*h/mL and the null hypothesis that the Arm B mean minus the Arm A mean is above 0 ug\*h/mL, i.e., that the two groups are not equivalent, in favor of the alternative hypothesis that the means of the two treatments are equivalent, assuming that the expected difference in means is -20 ug\*h/mL, the standard deviation of differences,  $s_d$ , is 20 ug\*h/mL, and that each test is made at the 5% level.

It is expected that approximately 1 patient per month may enroll onto this trial. Thus, to enroll 12 evaluable patients, it is anticipated that one year may be required. To allow for the possibility of a small number of patients who do not have full measurements obtained based on both drug administrations, the accrual ceiling will be set at 14 patients.

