### 8.3 POPULATIONS FOR ANALYSIS

Modified intention to treat. Only patients who participated in both drug administrations and have blood draws on at least 3 of the 4 required dates for each of the two administrations.

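### Section 8.4.2 averages undefined AUC values over four visits, and 8.3 lets those visits differ between periods, so a visit missed in one period only can create a false within-patient formulation difference

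*Combined protocol and SAP*

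**What the plan says.** Section 8.1 defines the endpoint by period: "The primary measure of efficacy will be AUC for the first period of administration", built from the visits on Days 1, 3, 8 and 42, and then the same for the second period. That is one AUC per administration.

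Section 8.4.2 defines the analysis variable differently: "The average of the AUC values at the 4 determinations associated with each of the two drug administrations will be determined". The difference is then tested at the 0.05 level by a published non-parametric procedure for the two-period change-over design.

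Section 8.3 limits the analysis to patients who took both administrations and "have blood draws on at least 3 of the 4 required dates for each of the two administrations". It does not ask for the same dates in both periods.

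Section 5.1 gives the late sampling times as "and 8 hours (Day 1), 24h (Day 2), 48h (Day 3), 168h (Day 8), and Day 42 post-dose", which makes five dates. It adds that "PK parameters derived from plasma concentration-time data may include" AUC among others. It gives no interval, trapezoid rule, extrapolation rule or rule for a missed sample.

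Section 8.2 expects that "the actual difference between the formulations may be a decline of approximately 10" per cent, about 20 ug*h/mL. It sets equivalence limits of -40 and 0 for the difference (the upper one worded as "the null hypothesis that the Arm B mean minus the Arm A mean is above 0"), with an SD of differences of 20 and 12 evaluable patients. It does not say which AUC these figures describe.

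**The concern.** A visit after Day 1 yields a concentration. An AUC at that visit has to be defined, as the area up to the visit, the area since the previous visit, or something else. The plan does not choose, and the choices behave differently. Cumulative areas count early exposure up to four times and late exposure once, so their average is not total exposure. Interval areas average to a quarter of the total, but only when all four are present.

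A crossover relies on measuring the same quantity twice in each patient. Under 8.3 a patient can contribute a four-visit average for one formulation and a three-visit average for the other, and the two differ even if the formulations are identical. Section 8.2 foresees a small number of patients with incomplete measurements, so the situation is expected.

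**Working it through.** **1. The plan's own figure.** Inputs from 8.2: limits -40 and 0, expected difference -20, SD of differences 20, 6 + 6 patients, 5% per test. The standard error is 20/√12 = 5.77. Exact power of two one-sided t tests is 88.4% with 10 degrees of freedom and 88.9% with 11. The smallest balanced total reaching 80% is 12 (10 patients give 78.4%). The sample size is therefore reproduced, with 80% read as at least 80%.

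**2. Illustrative profile.** Section 1.2.2 supplies Cmax 5.3 ug/mL at 1 h and AUCinf 292 ug*h/mL (fasted arm of the food-effect study), half-life 5.8 days, and a 7-day AUC of 185 for fasted capsules. Combining these sources is an assumption. The fitted curve, with t in hours, is

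C(t) = 4.618·exp(-0.0994t) + 1.230·exp(-0.00498t) - 5.848·exp(-4.02t).

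Its cumulative AUCs at 8, 24, 48, 168 and 1,008 h are 33.7, 68.5, 97.1, 185.0 and 290.4 ug*h/mL.

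**3. Cumulative reading, identical formulations.** It is unclear whether the Day 1 value stops at 8 h or takes in the 24 h sample, so both are shown. The remaining cumulative values are taken as unaffected by the gap.

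| Missed in one period | Day 1 to 24 h | Day 1 to 8 h |
|---|---|---|
| None | 641.0/4 = 160.3 | 606.2/4 = 151.6 |
| Day 42 | 350.6/3 = 116.9; shift -43.4 (-27.1%) | 315.8/3 = 105.3; shift -46.3 (-30.5%) |
| Day 8 | 456.0/3 = 152.0; shift -8.3 | 421.2/3 = 140.4; shift -11.2 |
| Day 3 | 543.9/3 = 181.3; shift +21.1 | 509.1/3 = 169.7; shift +18.2 |

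Over other profiles fitted to the cited figures, a missed Day 42 shifts the average by 25.6 to 48.6 ug*h/mL (-16% to -34%).

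**4. Other readings, same profile.**
- Interval AUCs, all visits present: 290.4/4 = 72.6, proportional to total exposure and so harmless.
- Interval AUCs, Day 42 missed: 185.0/3 = 61.7, or -15.1%. Other profiles can give a positive shift.
- Interval AUCs, Day 3 or Day 8 missed and merged into the next interval: three values carry the same total, so the average rises by about 4/3 - 1 = 33% or more.
- The single AUC of 8.1, ended at the last sample, Day 42 missed: 185.0 against 290.4, or -36.3%.
- AUC extrapolated to infinity without Day 42, linear-up/log-down on the scheduled samples: 289.4 against 296.0 with all samples (-2.2%) if the slope uses the last two points, and 269.3 (-9.0%) if it uses the last three.

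**5. Trial level, one missed Day 42, cumulative reading.** The mean moves by 25.6/12 = 2.1 to 48.6/12 = 4.1 ug*h/mL, about a tenth of the 40 limit at most. A single shift d adds d²/12 to the expected sample variance of the differences. For d = 43.4 to 46.3 the SD goes from 20 to √(400 + 157) = 23.6 or √(400 + 179) = 24.1. Simulated power of the two one-sided t tests, with the 8.2 values applied to the averaged variable by assumption:

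| Patients | Complete | One miss |
|---|---|---|
| 12 (6 + 6) | 88-89% | 67-83% |
| 14 (7 + 7) | 94% | 81-91% |

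The false-positive rate of a two-sided rank test of no difference, taken as the 8.4.2 test, is 4.1% with complete data, 4.1-4.2% with one miss and 5.8-7.1% with two misses on the same formulation.

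**6. The margin.** Section 8.2 equates 10% with about 20 and 20% with about 40, which implies a reference AUC near 200. Against the AUCs in 1.2.2, 40 is 40/185 = 21.6%, 40/237 = 16.9% or 40/292 = 13.7%.

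**The case against.** The best defence is that 8.4.2 is loose wording for the single AUC of 8.1, that 8.3 is a population rule and not a calculation rule, and that the 24 h sample belongs to the Day 1 admission described in 3.1. On that view a missed Day 3 or Day 8 costs almost nothing under a log-linear rule. Section 5.1 also names non-compartmental analysis with half-life and clearance, so extrapolation to infinity may be in mind, and it would largely repair a missed Day 42 in the profile above. These points limit the harm. They do not remove it, because the plan specifies neither the interpolation nor the extrapolation, and 8.4.2 as written prescribes an average.

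A reader might infer that every missed visit creates a false difference. The documents do not support that: size and sign depend on the AUC reading and on the visit, and some cases are near zero. A reader might also infer that the planned primary test loses the power shown above. It does not follow. Section 8.4.2 prescribes a test of difference, whose false-positive rate hardly changes with one miss, and the power figures belong to an equivalence test on the 8.2 assumptions. Whether a difference test can support bioequivalence is a separate question. Finally, the ceiling of 14 in 8.2 is a real reserve: at 14 patients one miss leaves power at 81-91%.

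**Conclusion.** The point holds as a conflict of definition with a practical consequence. Sections 8.1 and 8.4.2 name different primary variables, the second is undefined, and 8.3 permits unmatched visits, so a visit missed in one period only can create a false within-patient difference. In the illustrative profile, read cumulatively, a missed Day 42 gives about -43 to -46 ug*h/mL for that patient, a missed Day 3 +18 to +21 and a missed Day 8 -8 to -11. At trial level one miss is mainly added noise: 2 to 4 ug*h/mL on the mean, and a loss of power for an equivalence conclusion. Misses concentrated on one formulation would also bias the comparison. The sizes rest on profiles built from figures of several cited studies and on applying the 8.2 SD to the averaged variable. The textual conflict rests on neither. It should be fixed before analysis.

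**What to change.** Delete the averaging sentence in 8.4.2. In 8.1 and 8.4.2 state that:
- the primary variable is one enzalutamide AUC per administration, from 0 to Day 42, computed from all scheduled samples including 24 h by the linear-up/log-down rule;
- for each patient both AUCs use only the sampling times available in both periods and end at the last common time;
- the comparison stays on the difference scale of 8.2 and 8.4.1;
- AUC extrapolated to infinity is reported as a sensitivity analysis, with the rule for choosing terminal points.

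In 8.2 state which AUC the 20% and 40 ug*h/mL margin refers to, and rerun the power if the expected difference or SD changes with it.

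Two further changes are not needed. Test/reference ratios go beyond this defect. Filling a missed Period 1 Day 42 with the Period 2 pre-dose sample should be left out or given a time limit, since 3.1 sets only a minimum: "Following a minimum 42-day washout period, subjects will be crossed over in Period 2".

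The cost is text in 8.1, 8.2 and 8.4.2 and no new samples. The drawback is that a patient with a missed visit contributes an AUC over a shorter interval or from fewer samples. On the difference scale this shrinks his contribution: in the profile above a true 10% deficit is 29.0 ug*h/mL to Day 42 (0.1 × 290.4) but 18.5 to 168 h (0.1 × 185.0). If Day 42 is missed in one period and Day 8 in the other, both AUCs end at 48 h and it is 9.7 (0.1 × 97.1). The extrapolated sensitivity analysis would show whether this matters.

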## **1 INTRODUCTION**

### **1.1 STUDY OBJECTIVES**

#### **1.1.1 Primary Objective**

- To evaluate the bioequivalence of two oral formulations of enzalutamide following a single 160 mg dose in male subjects with prostate cancer

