### 8.4 STATISTICAL ANALYSES

#### 8.4.1 General Approach

The difference in the AUCs will be calculated following a published non-parametric approach for analyzing data from two-period cross-over studies:

Koch GG "The Use of Non-parametric methods in the statistical analysis of the two-period change-over design. *Biometrics* 28: 577-584 (1972).

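### The primary analysis in section 8.4.2 tests for a difference in AUC, not for equivalence, so it cannot answer the bioequivalence objective

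*Combined protocol and SAP*

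**What the plan says.** - **Section 1.1.1 (objective).** The sole primary objective is "To evaluate the bioequivalence of two oral formulations of enzalutamide following a single 160 mg dose".
- **Section 8.2 (design).** Bioequivalence is tied to "less than a 20% decrease in the AUC for the test version vs. the standard formulation", put at roughly 30-40 ug\*h/mL. The power statement uses two null hypotheses: that liquid minus capsule is below -40, and "the null hypothesis that the Arm B mean minus the Arm A mean is above 0". Rejecting both is "in favor of the alternative hypothesis that the means of the two treatments are equivalent", and "each test is made at the 5% level". The inputs are an expected difference of -20, an SD of differences of 20, and 6 patients per sequence, for 80% power.
- **Section 8.4.1 (method).** "The difference in the AUCs will be calculated following a published non-parametric approach", with a citation to a 1972 paper on two-period change-over designs.
- **Section 8.4.2 (primary analysis).** The AUC values for each administration are averaged, and "the difference assessed for statistical significance at the 0.05 level using the non-parametric procedures identified" in that paper.

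Section 8.1 is headed as the statistical hypotheses, but it restates the objective and names AUC without giving a hypothesis or limit. Sections 8.4.3 to 8.4.9 add no equivalence rule.

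**The concern.** A test for a difference and a test for equivalence ask different questions. A significant difference does not refute equivalence, because it may lie well inside the limits. A non-significant one does not establish equivalence, because the estimate may simply be imprecise. Section 8.4.2 does not state its null hypothesis, its sidedness or what either outcome implies for bioequivalence. Two analysts could follow it correctly and report opposite conclusions from the same data.

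The trial was designed to conclude equivalence when the liquid gives about 10% less exposure. That is also a case in which a difference test will usually be significant. If the rule is settled only after the data are seen, the answer to the trial's only primary question is open to challenge.

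**Working it through.** **Inputs, all from section 8.2:** N = 12 (6 per sequence), SD of differences 20, expected difference -20, limits -40 and 0, 5% per test. All AUC values below are in ug\*h/mL.

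**Assumptions, not in the documents:** the 8.4.2 test is two-sided; the cited method takes the form of a rank-sum test on within-patient period differences; data are normal; there is no period effect; and the SD and limits of 8.2 apply to the AUC quantity analysed.

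**Step 1. The plan's own sample size.** The standard error is SD/√N = 20/√12 = 5.77, with N - 2 = 10 degrees of freedom. Each one-sided 5% test uses t = 1.812. Equivalence is concluded if estimate - 1.812 × SE is above -40 and estimate + 1.812 × SE is below 0, which is the same as the 90% confidence interval lying inside (-40, 0). Integrating over the distribution of the estimated SD gives power of 78.4% at N = 10 and 88.4% at N = 12. So 12 is the smallest balanced size that reaches 80%. The sample size reproduces, and the stated 80% is best read as a target.

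**Step 2. The 8.4.2 test beside the 8.2 tests** (N = 12, SD 20). The two-sided 0.05 t test uses t = 2.228 on 10 degrees of freedom. The rank-sum figures are simulated, 6 against 6.

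| True difference | Significant, t | Significant, rank-sum | 8.2 equivalence tests pass |
|---|---|---|---|
| -40 | 99.999% | 99.99% | 5.0% |
| -20 | 87.6% | 83% | 88.4% |
| 0 | 5.0% | about 4% | 5.0% |

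The difference test gives nearly the same answer at -20 and at -40. If a non-significant result were read as equivalence, the planned scenario would succeed in only 100 - 87.6 = 12% (t) to 100 - 83 = 17% (rank-sum) of trials.

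**Step 3. One dataset, two conclusions.** Suppose the trial observes exactly what it expects: difference -20, SD 20. The 90% interval is -20 ± 1.812 × 5.77 = -20 ± 10.5, or -30.5 to -9.5. This lies inside (-40, 0), so 8.2 concludes equivalence. The test statistic is -20/5.77 = -3.46, beyond 2.228, so 8.4.2 reports a significant difference. This is typical: at a true difference of -20, 81.9% of simulated trials do both and 88.4% pass, so 0.819/0.884 = 93% of passing trials are also significant.

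**Step 4. False reassurance.** At a true difference of -40 and SD 20, a non-significant result occurs in about 0.001% of trials (t), which is negligible. It reaches 12% (t) to 17% (rank-sum) only at an assumed SD of 40.

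**Step 5. Why 8.2 cannot be copied unchanged.** With limits (-40, 0), identical formulations sit on the upper limit and pass only 5.0% of the time; a true difference of -10 passes 48.7%. With the lower limit kept at -40:

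| Upper limit | Pass at -20 (t interval) | Pass at 0 (t interval) |
|---|---|---|
| 0 | 88.4% | 5.0% |
| +20 | 94.2% | 94.2% |
| +30 | 94.2% | 99.9% |
| +40 | 94.2% | about 100% |

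A Hodges-Lehmann interval from the within-patient period differences (attained level 90.7%) passes 84% at -20 with the present limits and 92% with an upper limit of +20 to +40.

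**The case against.** The best reply is that section 8.2 supplies the hypotheses and 8.4.2 only the method. Both sit in the same chapter and both use 5%. There is also a real overlap: because the upper limit in 8.2 is 0, a significant negative difference under 8.4.2 does reject the upper null. But the test against -40, which bounds the loss of exposure, appears nowhere in 8.4, and 8.4.2 describes a single assessment of the difference without mentioning 8.2. A reader would have to infer the missing test and how to shift a rank method to that limit.

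A second reply is that this is called a pilot (sections 1.2.4 and 3.1) and, under section 10, is not meant to support labelling. That tempers the consequence. It does not remove the gap, since bioequivalence is the primary objective and the trial is powered for it.

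Some cautions about the power figures stand:

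- **Lower limit.** The assurance of adequate power rests on -40. Section 8.2 also speaks of 30-40 and of less than 20%. Against the fasted capsule mean of 185 in section 1.2.2, 20% is 37. At a true difference of -20, limits of ±37 give 86% power, but ±30 gives only 49%.
- **Meaning of the SD.** Section 8.2 calls 20 the SD of differences, the reading used here. If it were a within-patient SD, power at -20 would be 48% with the present limits and 74% with ±40.
- **Rank figures.** They depend on the assumed rank-sum form of the cited method.

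None of these changes the conclusion about 8.4.2.

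**Conclusion.** The concern holds and must be fixed. The stated primary analysis is the wrong kind of test for the stated objective, and no other part of 8.4 supplies a rule for concluding bioequivalence. On the plan's own figures the test is significant in 83-88% of trials in the case the trial is sized to call equivalent and in more than 99.9% at its non-equivalence limit, where the 8.2 tests pass 88.4% and 5%. The main harm is an uninterpretable or contradictory result. False reassurance at -40 is negligible unless the SD is far above 20.

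The textual gap depends on no assumption. The percentages rest on the assumptions listed with the calculation.

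**What to change.** 1. **Section 8.4.2 (and 8.4.1).** State that equivalence is concluded only if the 90% confidence interval for liquid minus capsule AUC lies wholly inside the limits given in 8.2. Use the crossover t interval or, to keep a rank method, the Hodges-Lehmann interval from within-patient period differences. Define a single AUC per administration in place of the averaged values, so that the quantity analysed is the one the limits refer to.
2. **Section 8.2, limits.** In the same edit, replace the upper limit of 0 with a justified limit above 0. Symmetric limits of -40 to +40 are one option. This is an assumption for the sponsor to justify: section 8.2 equates 10% with about 20 ug\*h/mL, so 40 is about 20% on that scale. Confirm the lower limit and the meaning of the SD at the same time.
3. **Section 8.2, power.** Restate power at a difference of -20, SD 20 and N = 12. It is 88.4% with the present limits or 94.2% with -40 to +40 for the t interval, and 84% or 92% for the rank interval.

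The cost is wording in 8.2, 8.4.1 and 8.4.2, plus the sponsor's justification of the upper limit. No patients, samples or visits are added: with a lower limit of -40 and an SD of differences of 20, N = 12 keeps about 92% power or more at -20 for any upper limit from +20 to +40. If the lower limit moves towards -30 or the SD proves larger, the sample size must be revisited.
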